16.2 Laboratory data

The summary of lab data will only include on treatment data, which are defined as those lab assessments after the first dose of secukinumab in core and on or before last dose + 84 days.

The summary of laboratory evaluations will be presented for hematology, chemistry and urinalysis. In addition to the individual laboratory parameters the ratios “total cholesterol / HDL” and “apolipoprotein B / apolipoprotein A1” will be derived and summarized.

For urinalysis frequency tables will be presented in this final lock.

Descriptive summary statistics for the change from baseline to each study visit in extension will be presented. These descriptive summaries will be presented by laboratory test and treatment dose. Baseline data from core study will also be included in these summaries. Change from baseline will only be summarized for subjects with both baseline and post baseline values and will be calculated as:

$$\text{change from baseline} = \text{post baseline value} - \text{baseline value}$$

For each parameter, the maximum change (maximum decrease and maximum increase) from baseline, if appropriate for each study phase, will be analyzed.

In addition, shift tables will be provided for all parameters to compare a subject's baseline laboratory evaluation relative to the visit's observed value. For the shift tables, the normal laboratory ranges will be used to evaluate whether a particular laboratory test value was normal, low, or high for each visit value relative to whether or not the baseline value was normal, low, or high. If appropriate, the shifts to the most extreme laboratory test value within the entire treatment period will be presented as well (including category “high and low”). These summaries will be presented by laboratory test and treatment dose.

Reported laboratory assessments with either a less than or greater than sign (“<” or “>”) will be used for analysis after removal of the sign and conversion to standard unit. These laboratory data will be displayed in listings using the standard unit with the reported sign (“<” or “>”).

The following laboratory parameters will be analyzed with respect to numerical Common Terminology Criteria for Adverse Events (CTCAE) grades, given in [Table 16-2](#): hemoglobin, platelets, white blood cell count, neutrophils, lymphocytes, creatinine, total bilirubin (TBL), gamma-glutamyl transferase (GGT), alanine aminotransferase (ALT), aspartate aminotransferase (AST), alkaline phosphatase (ALP), glucose, cholesterol, triglycerides (TG).

These summaries will be split into hematology and chemistry for study level reports and the pooled summary of clinical safety.

Table 16-1 CTCAE grades for laboratory parameters to be analyzed

CTCAE v4.0 Term	Grade 1	Grade 2	Grade 3	Grade 4
HGB decreased (Anemia)	<LLN – 100 g/L	<100 – 80 g/L	<80 g/L	Life-threatening consequences; urgent intervention indicated
Platelet count decreased	<LLN – 75.0 x10e9 /L	<75.0 - 50.0 x10e9 /L	/L	<25.0 x 10e9 /L
White blood cell decreased	<LLN - 3.0 x 10e9 /L	<3.0 - 2.0 x 10e9 /L	<2.0 - 1.0 x 10e9 /L	<1.0 x 10e9 /L
Neutrophil count decreased	<LLN - 1.5 x 10e9 /L	<1.5 - 1.0 x 10e9 /L	<1.0 - 0.5 x 10e9 /L	<0.5 x 10e9 /L

CTCAE v4.0 Term	Grade 1	Grade 2	Grade 3	Grade 4
Lymphocyte count decreased	<LLN - 0.8 x 10e9/L	<0.8 - 0.5 x 10e9 /L	<0.5 - 0.2 x 10e9 /L	<0.2 x 10e9 /L
Creatinine increased*	>1 - 1.5 x baseline;	>1.5 - 3.0 x baseline;	>3.0 baseline;	
	>ULN - 1.5 x ULN	>1.5 - 3.0 x ULN	>3.0 - 6.0 x ULN	>6.0 x ULN
TBL increased	>ULN - 1.5 x ULN	>1.5 - 3.0 x ULN	>3.0 - 10.0 x ULN	>10.0 x ULN
GGT increased	>ULN - 2.5 x ULN	>2.5 - 5.0 x ULN	>5.0 - 20.0 x ULN	>20.0 x ULN
ALT increased	>ULN - 3.0 x ULN	>3.0 - 5.0 x ULN	>5.0 - 20.0 x ULN	>20.0 x ULN
AST increased	>ULN - 3.0 x ULN	>3.0 - 5.0 x ULN	>5.0 - 20.0 x ULN	>20.0 x ULN
ALP increased	>ULN - 2.5 x ULN	>2.5 - 5.0 x ULN	>5.0 - 20.0 x ULN	>20.0 x ULN
Glucose increased (Hyperglycemia)	>ULN - 8.9 mmol/L	>8.9 - 13.9 mmol/L	>13.9 - 27.8 mmol/L	>27.8 mmol/L
Glucose decreased (Hypoglycemia)	<LLN - 3.0 mmol/L	<3.0 - 2.2 mmol/L	<2.2 - 1.7 mmol/L	<1.7 mmol/L
Cholesterol high	>ULN - 7.75 mmol/L	>7.75- 10.34 mmol/L	>10.34-12.92mmol/L	>12.92 mmol/L
Hypertriglyceridemia	1.71 - 3.42 mmol/L	>3.42 - 5.7mmol/L	>5.7 - 11.4 mmol/L	>11.4 mmol/L

*Note: for "creatinine increased" the baseline criteria do not apply

Shift tables will be presented comparing baseline laboratory result (CTCAE grade) with the worst results (expressed in CTCAE grade) during the entire treatment period. Of note, baseline will be defined as last assessment prior to first dosing in initial treatment phase. Subjects with abnormal laboratory values will be listed and values outside the normal ranges will be flagged.

Summaries for newly occurring or worsening clinically notable lipid abnormalities will also be provided cumulatively for each of the following parameters and categories:

- HDL:
 - <=LLN
 - <0.8 x LLN
- LDL, cholesterol, triglycerides:
 - >=ULN
 - >1.5 x ULN
 - >2.5 x ULN

Newly occurring or worsening liver enzyme abnormalities will also be summarized based on the event criteria given in [Table 16-3](#) below:

Table 16-2 Liver-related events

Parameter	Criterion
ALT	>3xULN; >5xULN; >8xULN; >10xULN, >20xULN
AST	>3xULN; >5xULN; >8xULN >10xULN; >20xULN
ALT or AST	>3xULN; >5xULN; >8xULN >10xULN; >20xULN
TBL	>1.5xULN, >2xULN, >3xULN,
ALP	>2xULN, >3xULN. >5xULN
ALT or AST & TBL	ALT or AST>3xULN & TBL >2xULN; ALT or AST >5xULN & TBL >2xULN; ALT or AST >8xULN & TBL >2xULN; ALT or AST >10xULN & TBL >2xULN
ALP & TBL	ALP >3xULN & TBL >2xULN ALP >5xULN & TBL >2xULN

For a combined criterion to be fulfilled, all conditions have to be fulfilled on the same visit. The criteria are not mutually exclusive, e.g. a subject with ALT = 6.42xULN is counted for ALT >3xULN and ALT>5x ULN.

Individual subject data listings will be provided for subjects with newly occurring or worsening liver enzyme and lipid parameters abnormalities, or for subjects with newly occurring or worsening after baseline CTCAE grades.

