Control drug	Drugs(s) used as a comparator to reduce assessment bias, preserve blinding of investigational drug, assess internal study validity, and/or evaluate comparative effects of the investigational drug
Enrollment	Point/time of subject entry into the study; the point at which informed consent must be obtained (i.e. prior to starting any of the procedures described in the protocol)
Epoch (period)	The planned stage of the subjects' participation in the study. Each epoch serves a purpose in the study as a whole. Typical epochs are: determination of subject eligibility, wash-out of previous treatments, exposure of subject to treatment or to follow-up on subjects after treatment has ended.
Inadequate response to TNF α	Active disease despite stable treatment with anti-TNF α for at least 3 months at an approved dose or for at least one dose in the case of lack of tolerance.
Investigational drug	The drug whose properties are being tested in the study; this definition is consistent with US CFR 21 Section 312.3 and is synonymous with "investigational new drug" or "investigational medicinal product."
Investigational treatment	All investigational drug(s) whose properties are being tested in the study as well as their associated treatment controls. This includes any placebos, any active controls, as well as approved drugs used outside of their indication/approved dosage or tested in a fixed combination. Investigational treatment generally does not include other treatments administered as concomitant background therapy required or allowed by the protocol when used within approved indication/dosage
Medication number	A unique identifier on the label of each investigational/study drug package in studies that dispense medication using an IRT system
Premature subject withdrawal	Point/time when the subject exits from the study prior to the planned completion of all investigational/study treatment administration and all assessments (including follow-up)
Randomization number	A unique identifier assigned to each randomized subject, corresponding to a specific treatment arm assignment
Stop study participation	Point/time at which the subject came in for a final evaluation visit or when study/investigational treatment was discontinued whichever is later
Study drug/ treatment	Any single drug or combination of drugs administered to the subject as part of the required study procedures; includes investigational drug (s), active drug run-ins or background therapy

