5.2 Treatment groups

Unless otherwise specified, the summaries will be performed by the treatment sequence.

- Efficacy:

- AIN457 10 mg/kg - 75 mg -150 mg
- AIN457 10 mg/kg - 150 mg
- Placebo - AIN457 75 mg – 150 mg
- Placebo - AIN457 150 mg
- Any AIN457 75 mg
- Any AIN457 150 mg

After week 52 the combination of assigned treatments will also be shown as follows:

- AIN457 75 mg & Placebo - AIN457 75 mg
- AIN457 150 mg & Placebo - AIN457 150 mg

Tables on MMRM or MI estimates will be summarized only for the AIN457 10 mg/kg - 150 mg originally randomized group.

- Safety
 - Any AIN457 75 mg
 - Any AIN457 150 mg
 - Any AIN457

Placebo treatment group will be displayed only in safety listings and in in-tex safety tables.

6 Subgroup definitions

The primary endpoint(s) and secondary endpoints will be evaluated by TNF-alpha inhibitor status.

7 Assessment windows, baseline and post baseline definitions, missing data handling

Baseline and post-baseline definitions

In general [REDACTED], a *baseline* value refers to the last measurement made prior to administration of the first dose of study treatment. A post-baseline value refers to a measurement taken after the first dose of study treatment.

For X-ray, a baseline value is the last measurement prior to dosing if available, or the first value within 30 days post dosing if no other value is available prior to dosing.

[REDACTED]

For post baseline visit -windows during the core study the following applies (unless otherwise specified):

For quantitative variables, the closest to the actual visit is chosen (if two assessment have the same distance, then the earlier now will be chosen)/

For qualitative variables, the worst record is selected. It is noted that in the analysis performed, worst case is always well defined (e.g., for urine protein values “+” and “++” the worse case is defined as “++”).

Analysis visit windows

Analysis visit windows will be used for the data that is summarized by visit; they are based on the study evaluation schedule and comprise a set of days around the nominal visit day. For any assessment, there are protocol defined scheduled visits around which analysis visit windows were created to cover the complete range of days within the study. The analysis visit windows and rules for dealing with multiple measurements within the windows are described in [Section 19.1](#).

For visits that occur after week 104, the recorded nominal visit data will be considered.

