Additional analysis will be based on the imputed responses only for the AIN457 150 mg group.

[figure not shown]
The percentage of subjects (and the 95% CI) experiencing ASAS40 response after up-titration will be presented in separate tables (observed data). Patients who had at least 1 dose of the up-titrated dose will be included.

16 Safety evaluation

Safety analyses will be done on the safety set.

Analysis of adverse events will be based on treatment emergent events, which are defined as events started after the first dose of study treatment in core study or events present prior to the first dose of study treatment in core study but increased in severity based on preferred term and within last dose + 84 days.

Other safety variables will be based on on-treatment events, which are defined as any events that happened after first dose of study treatment and within last dose + 84 days.

Summaries (other than by visit analysis) will be presented cumulatively from core and extension. For subjects who switched from placebo to secukinumab in the core study, their data prior to switch will not be reported. Safety on placebo will be based on the core study and will be reported in the in-text outputs and study listings.

Unless otherwise mentioned, by visit analysis will include the following visits: Baseline visit from core, Week 104E1 visit and all visits in extension. Summaries will be performed for all the events that happened within the last dose + 84 days.

Safety analyses will be performed on treatment received or actual treatment as described below:

The actual treatment or treatment received for summaries of safety data will differ to the treatment assigned at randomization if a subject received the wrong treatment during the entire study or if the subject up-titrated to a higher dose..

Subjects who switch treatment during the study (e.g. from placebo to active treatment, or escalated the dose) will be counted to both groups using the corresponding start and stop exposure date.

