16.1 Adverse events

The crude incidence of treatment emergent adverse events on secukinumab (i.e. events started after the first dose of secukinumab in core study or events present prior to the first dose of secukinumab but increased in severity based on preferred term and within 84 days after last dose of secukinumab) will be summarized by primary system organ class and preferred term for the entire treatment period. CIs for the crude rate will be derived as described in [Section 19.3.3](#).

In addition, exposure time-adjusted rates (incidence rate) including 95% CIs will be provided for selected terms for the entire treatment period (see [Section 19.3.5](#)) to adjust for differences in exposure.

Adverse events reported will be presented in descending frequency according to the incidence in total secukinumab group (combining all secukinumab treatment groups) starting from the most common event.

Summary statistics will be provided by primary system organ class and preferred term for the entire treatment period for all TEAEs, for serious TEAEs, for deaths, for TEAEs causing treatment discontinuation, for TEAEs possible related to study treatment, for TEAEs leading to temporary dose interruptions, for other serious or clinically significant treatment emergent adverse events or related discontinuations, for SPP risks and for adjudicated major adverse cardiovascular events (MACE). Additionally, summary statistics by 26 and 52 weeks intervals will be displayed reflecting the long term safety. For these tables the AEs will be counted only at the interval they were initially observed. If another AE with the same PT is starting again in a following time interval then it will be counted again at this interval.

Summaries (crude incidence only) will be presented for TEAEs by maximum severity as well. If a particular AE 'severity' is missing, this variable will be listed as missing and treated as missing in summaries.

If a subject reported more than one adverse event with the same preferred term, the adverse event with the greatest severity will be presented. If a subject reported more than one adverse event within the same primary system organ class, the subject will be counted only once with the greatest severity at the system organ class level, where applicable.

Adverse events separately by SMQ according to MedDRA using a narrow search will also be reported..

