Exposure adjusted incidence rates for TEAEs by SMQ and preferred term, for selected lower lever risk terms based on TEAEs, serious adverse events, SPP risks and MACE, common and/or very common AE will be summarized by primary system organ class for the entire period.

The following AE terms are defined as lower lever risk terms:

- Dyspnea (PT)
- Seasonal allergy (PT)
- Colitis ulcerative (PT)
- Crohn's disease (PT)
- Inflammatory bowel disease (PT)
- Upper respiratory tract infections (HLT)
- Candida infections (HLT)
- B-cell lymphoma (PT)
- Bladder transitional cell carcinoma (PT)
- Breast cancer (PT)
- Lymphoma (PT)
- Malignant melanoma (PT)
- Dermatitis (PT)
- Eczema (PT)
- Rash(PT)
- Leukopenia (PT)
- Neutropenia (PT)
- White blood cell count decreased (PT)
- Dyspnea (PT)
- Seasonal allergy (PT)
- Diarrhea Hemorrhagic (PT)
- Squamous cell carcinoma (PT)
- Urticarial (PT)
- Uveitis (PT)
- Drug related hepatic disorders – severe events only (SMQ)(broad)
- Liver related investigations, signs and symptoms (SMQ) (broad)

The above list maybe modified based on the clinical team's advice.

As selection criterion for the common AE is the frequency of them of at least 2% in the initial treatment period (up to week 16) or IR of at least 5 during the entire treatment period as observed in the Any AIN457 group. The very common AE are defined in Core Data Sheet V2.1 (17-Mar-2017), Table 7.1. These include the following PTs: Nasopharyngitis, Upper respiratory tract infection, Rhinitis, Pharyngitis, Oral herpes, Rhinorrhoea, Diarrhea, Urticaria.

The incidence of AEs will be presented per 100 subject years of exposure.

The MedDRA version used for reporting the study will be described in a footnote.

If needed, follow-up period summaries will be done for all subjects in follow-up in this extension study (completers and early discontinuations).

AE listings will be limited to deaths, non-fatal SAEs, AE requiring treatment discontinuations and adjudicated MACE events.

Algorithms for date imputations in the AE listings are provided in PDS.

When adjudication is required of major cardiovascular events, a summary of those types of events as reported by the investigator and confirmed by adjudication will be provided.

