Group 1: [REDACTED], Cardiovascular panel,

Group 2: X-Ray

Group 3: Lipids

Group 4: weight

Group 5: ECG,

Group 6: Physical exam, Vital signs

Group 7: Hematology, Blood chemistry, Urinalysis, Patient's global assessment of disease activity, Patient's assessment of spinal pain, [REDACTED], [REDACTED]

[REDACTED], Urine pregnancy test

Group 8: [REDACTED]

* The first administration of study treatment (first dose in core) is defined as Day 1.

The following rules are used to determine the window for an applicable visit post baseline: “Lower limit” = “upper limit of prior applicable visit” + 1. “Upper limit” = “target of current visit” + integer part of (“target of next applicable visit” – “target of current visit”)/2. Lower limit of the first applicable visit is always 2.

The mapping described above applies to all core visits (not just scheduled visits). Repeat and/or unscheduled visits (which will be numbered in the database according to new NCDS standards) will be mapped for analysis purposes in the same way as scheduled visits. This leaves the possibility, then, for multiple measurements within an analysis window. The following conventions will be used to determine the appropriate measurement to be summarized in the event of multiple measurements within a visit window.

Table 19-2 Rules for flagging variables

Timing of measurement	Type of data	Rule
Baseline	All data	The last measurement made prior to administration of the first dose of study treatment – note this may include measurements taken on the day of randomization (e.g. lab). Baseline assessments scheduled for and captured on Day 1 will be considered baseline measurements regardless of the time of assessment. If a patient did not receive any dose of study treatment then the randomization date will be used.
Post-baseline efficacy during the core study phase	All data	
For visits without switch of treatment in the window, the measurement closest to the target will be used. In the event two measurements are taken equally apart (e.g. 1 before target date and 1 after) the first one will be used.
Post-baseline safety during the core study phase	Summary visit information (e.g. lab, ECG, etc.)	
For visits without switch of treatment in the window, the measurement closest to the target will be used. In the event two measurements are taken equally apart (e.g. 1 before target date and 1 after) the first one will be used.

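### For placebo switchers, newly occurring or worsening laboratory and vital-sign abnormalities are judged against the pre-core baseline, so one that began on placebo and persists is counted as new on secukinumab

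*SAP*

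**What the plan says.** **Reference value.** SAP 16.2 sets a subject's baseline CTCAE grade against the worst grade over the entire treatment period and fixes the baseline: "Of note, baseline will be defined as last assessment prior to first dosing in initial treatment phase". SAP 16.1 describes the initial treatment period as running to Week 16, which places it in the core study. The general definition in SAP 7 agrees: a baseline "value refers to the last measurement made prior to administration of the first dose of study treatment". So does SAP 19.1: "The first administration of study treatment (first dose in core) is defined as Day 1". The protocol glossary counts "any placebos, any active controls" as investigational treatment, so for a subject randomised to placebo the first core dose is a placebo dose.

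**What is compared with it.** SAP 16.2 also summarises newly occurring or worsening lipid and liver abnormalities, and SAP 16.3 newly occurring notable vital signs. Neither section gives these summaries a reference of their own.

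**Which data count.** Laboratory summaries in SAP 16.2 start at the first secukinumab dose in core. SAP 4 and SAP 16 leave out the pre-switch data of subjects who moved from placebo to secukinumab. The safety columns in SAP 5.2 are Any AIN457 75 mg, Any AIN457 150 mg and Any AIN457. On switching, SAP 16 says: "Subjects who switch treatment during the study (e.g. from placebo to active treatment, or escalated the dose) will be counted to both groups", using each treatment's exposure dates.

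**Adverse events.** SAP 16.1 takes the first secukinumab dose as its reference and includes "events present prior to the first dose of secukinumab but increased in severity". The general wording in SAP 16 refers instead to the first dose of study treatment in core.

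**The concern.** For placebo switchers the reference value and the start of the counted data are separated by the whole placebo period. Anything that changed in that interval is invisible in the summaries, yet it is scored as a change on secukinumab.

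Low-threshold and slowly drifting parameters are the most exposed. Examples are cholesterol, LDL or triglycerides at or above the upper limit of normal, HDL at or below the lower limit, and systolic pressure of 140 mmHg or more. These rows are read as what appeared or worsened on the drug. Protocol 3.4 also relies on the two doses to describe safety and tolerability. An abnormality that arose before any secukinumab was given belongs in neither dose column as a new finding.

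**Working it through.** The plan gives no figure to reproduce here, so the check applies its rules to simple cases.

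**Step 1: follow a placebo switcher through the rules.** The reference is the last value before the first core dose (SAP 7, 16.2, 19.1). The counted values are those after the first secukinumab dose: for laboratory data by SAP 16.2, for vital signs by the SAP 16 exclusion of pre-switch data. Nothing visible resets the reference at the switch. An abnormality is new if the worst counted grade exceeds the reference grade.

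**Step 2: five cases** (0 = normal, 1 = abnormal; two assessments in each period).

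| Case | Core baseline | On placebo | After switch | New under SAP rule | New against last pre-secukinumab value |
|---|---|---|---|---|---|
| A: arises on placebo, persists | 0 | 1, 1 | 1, 1 | yes | no |
| B: arises on placebo, resolves before switch | 0 | 1, 0 | 0, 0 | no | no |
| C: arises after switch | 0 | 0, 0 | 1, 1 | yes | yes |
| D: present at core baseline, unchanged | 1 | 1, 1 | 1, 1 | no | no |
| E: present at core baseline, resolves, returns after switch | 1 | 1, 0 | 1, 1 | no | yes |

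Case A is wrongly counted, in the dose column and in Any AIN457. Case E is the reverse: the SAP rule misses an abnormality that returned on secukinumab. The two rules agree on the other three.

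**Step 3: possible size, on assumed rates only.** Per 100 placebo switchers, let q be the share newly abnormal at the switch, r the share of those still or again abnormal afterwards, and i the risk of true new onset in the rest.

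- Carry-over = 100 × q × r
- Truly new = 100 × (1 − q) × i
- SAP-rule count = the sum of the two

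Assume q = 2%, 5% or 10%; r = 30%, 50% or 80%; i = 2% or 5%.

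- Smallest carry-over share (q = 2%, r = 30%, i = 5%): 100 × 0.02 × 0.30 = 0.6; 100 × 0.98 × 0.05 = 4.9; total 5.5; share 0.6/5.5 = 11%.
- Largest share (q = 10%, r = 80%, i = 2%): 100 × 0.10 × 0.80 = 8.0; 100 × 0.90 × 0.02 = 1.8; total 9.8; share 8.0/9.8 = 82%.
- Over the whole grid the SAP-rule count runs from 2.6 to 12.5 per 100, and the truly new count from 1.8 to 4.9.

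This leaves out case E, which works the other way. In a column where placebo switchers make up a fraction s of subjects, the excess from carry-over is s × q × r. The documents give none of s, q, r or i.

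**Step 4: subjects escalated from 75 mg to 150 mg.** SAP 16 counts them in both dose groups by exposure dates, but the SAP does not say how the onset of a laboratory abnormality is dated. If the worst value on 150 mg is compared with the pre-core value, an abnormality that began on 75 mg and persists is new in both dose columns. If it is dated by first onset, it falls only in the 75 mg column. Either way it counts once in Any AIN457.

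**The case against.** The strongest case against runs as follows.

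- **Reach of the baseline sentence.** It directly governs only the CTCAE shift tables. That is correct. The lipid, liver and vital-sign rows take the pre-core reference from the general definition, part of which is blacked out, so an exception cannot be ruled out for them. For the CTCAE tables the visible text leaves no such doubt.
- **Adverse events as a precedent.** SAP 16.1 and SAP 16 word the adverse-event reference differently, so 16.1 alone cannot be called the SAP's rule. This stands. It is a reason to harmonise the two, and it leaves the laboratory rule as it is. Neither wording resets the reference at escalation.
- **Visibility.** Placebo safety appears in listings and in-text tables, and subjects with abnormal values are listed. That helps a careful reader, but pre-switch data of switchers are excluded from reporting, and the listings do not change what the summaries count as new.
- **A pre-treatment reference is sound for cumulative safety.** For escalated subjects this stands. Taking a value measured on 75 mg as baseline would remove from the 150 mg column abnormalities that the drug may have caused and that persist. It does not defend a pre-placebo reference, because the last value before secukinumab is also a pre-drug value and is closer in time.
- **Limited consequence.** SAP Table 16-1 gives these notable abnormalities crude incidence only, and no hypothesis is tested. This stands and sets the weight of the point.

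**Conclusion.** Wrong as written for placebo switchers, and minor. On the visible text, an abnormality that began on placebo and persists past the switch is scored as newly occurring or worsening on secukinumab. This is firm for the CTCAE shift tables. For the lipid, liver and vital-sign rows it rests on the general baseline applying without a redacted exception. Only abnormalities still or again present after the switch are affected. The size cannot be computed; the range of 0.6 to 8.0 extra cases per 100 placebo switchers depends entirely on the assumed rates.

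A reader might go further and infer that the rule always inflates the rates and builds a false dose-related signal against 150 mg. The documents do not support that:

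- Case E shows that individual subjects can be misclassified in the other direction.
- SAP 5.2 lists placebo sequences leading to both 75 mg and 150 mg, so placebo carry-over can enter both dose columns.
- Counting an abnormality as new under both 75 mg and 150 mg depends on an onset-dating rule that the SAP does not give, and it would not raise Any AIN457.
- The number of escalated subjects is not given, so no inflation of the 150 mg column can be put in figures.

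**What to change.** 1. In SAP 16.2 and 16.3, for subjects who switched from placebo, define the reference for newly-occurring-or-worsening and shift-to-worst summaries as the last value before the first secukinumab dose. Keep the core baseline for by-visit change tables.
2. State in the same place that the lipid, liver and vital-sign rows use this reference, so that it need not be inferred from SAP 7.
3. For subjects escalated from 75 mg to 150 mg, keep the pre-secukinumab reference. In the 150 mg column, flag or footnote abnormalities already present at the last assessment on or before the first 150 mg dose. SAP 19.1 already defines that before-up-titration measurement. Subjects in the placebo, 75 mg, 150 mg sequence need both items 1 and 3.
4. Harmonise the treatment-emergent wording of SAP 16 with that of 16.1.

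SAP 16.4 can stay as it is on this point, since most of its rows are absolute thresholds with no test for new occurrence.

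The cost is SAP wording, one extra derived flag and a footnote explaining that two reference values are in use. No new data are needed.
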